In 2012, Linville, Shamblin, and Ball interviewed 48 client participants and 5 staff members to get a better understanding of couples' experiences when participating in a conjoint treatment program for intimate partner violence. Participants reported benefits and changes in their lives from participating in the conjoint groups for intimate partner violence feeling they felt the experience increased safety, that they benefited from being in a group that supported one another working toward a common goal, an increased awareness of the role their behavior plays on their relationship, behavior changes such as being calmer, listening better, and taking better care of themselves, and finally learning tools for how to better communicate with their partners and handle relational stress.

The Contribution of the Current Study

While the literature on the effectiveness of couples therapy suggests that couples therapy can be effective in preventing and diminishing situational couple violence, these results are mostly based on self-report data. Therefore, they do not provide quantitative grounds for the link between couples therapy and decline in situational couple violence. The aim of this study is to investigate this link by monitoring psycho-physiological markers of emotion regulation along with self-report data. If successful, the results of this study will provide quantitative and objective evidence on the effectiveness of couple therapy. Furthermore, these results will provide preliminary data in uncovering the psycho-physiological mechanisms through which couple therapy reduces violent behavior.

Principal Investigator: [name]

Protocol Summary for IRB: Feasibility Study of Couple Therapy Treatment for Situational Couple Violence (IRB# 09-13-27)

Overall, this study has significance not only for the scientific community, as research on the effectiveness of conjoint therapy can pave the way for more comprehensive and large scale effectiveness studies, but for the individual participants, as they will be receiving quality treatment for a severe and potentially debilitating problem: violence within their intimate relationships.

Study Design & Objectives

Purpose

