The purpose of this study is to understand whether the couple therapy that is used in practice is effective in preventing situational couple violence. More specifically, we will focus on couples with mild to moderate forms of situational couple violence to investigate how couple therapy can be effective in preventing the escalation and recurrence of situational couple violence. For this purpose, the response of partners to therapy will be investigated by integrating self-report questionnaires and psycho-physiological markers of emotion. All couples who exhibit characteristics of characterological violence will be excluded from the study.

The change in partners' emotion regulation over the course of therapy will be measured using psycho-physiological markers of stress response. Using these measurements, the interplay between changes in violence and the emotion regulation of partners in relation to each other will be investigated in a dyadic (couple) context. More specifically, the following aims will be pursued to understand the relationship between couple therapy, emotion regulation, and violence:

Aim 1: Examine the associations between IPV and each partner's psychophysiological regulation in terms of Hypothalamic Pituitary Adrenal (HPA) activity and Parasympathetic Nervous System (PNS) activity. This aim will investigate whether dysregulation of HPA and PNS activity in each partner is correlated with the existence and intensity of IPV for the couple. Existence and intensity of IPV will be assessed using self and partner report questionnaires. HPA activity will be measured using salivary cortisol, and PNS activity will be measured using vagal tone and vagal regulation by using an eMotion Heart Rate Variability (HRV) sensor.

Aim 2: Examine the longitudinal effects of conjoint therapy on IPV and each partner's psychophysiological regulation in terms of HPA and PNS activity. This aim will investigate whether the reported intensity of IPV for couples decreases after couples start therapy and whether this change is correlated with regulation of HPA and PNS activity for each partner. This aim will examine the effect of couple therapy on each individual partner separately.

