Aim 3: Examine the longitudinal effects of partners' psychophysiological regulation on each other's psychophysiological regulation and on IPV. This aim will explore patterns of change in each partner's psychophysiological regulation as a function of their partner's psychophysiological regulation. More specifically, this aim will investigate whether couple therapy facilitates change by restructuring the relationship in such a way that the change in one partner's behavior helps the other partner regulate their emotions in a functional way.

Principal Investigator: [name]

Protocol Summary for IRB: Feasibility Study of Couple Therapy Treatment for Situational Couple Violence (IRB# 09-13-27)

Study Design

This study has a longitudinal design that requires therapy sessions over 8 weeks, with data collected at every visit. Couple therapy will be conducted using an attachment and affect regulation based therapy approach described below under “Couple Therapy”. Data will be collected in the form of self-report and partner-report measures, as well as physiological screening of the neuroendocrine system. These measures are described below under “Data Collection”. The flowchart for the design of the study is shown below.

After careful screening, eight couples will be enrolled in the study. The couples will be divided into two groups, each consisting of four couples. Distribution of participants to the two groups will be randomized. Group 1 will immediately begin 8 weeks of couple therapy and Group 2 will complete 8 weeks of couple therapy after an 8 week (+ or – 10 days) waiting period is completed.

The pre-test, post-test, and follow-up physiological data collection will be completed at the following times for couples beginning the 8 weeks of couple therapy:

- Baseline Pre-test: Before starting the therapy sessions.
- Post-test: One week (+ or – 5 days) after the end of the therapy session.
- Follow-up: Three months (+ or – 10 days) after the post-test.

The participants that are assigned to Group 2 will also complete the physiological data collection before starting the 8 week waiting period. When participating in the 8 week couple therapy Group, participants will complete a small number of assessments at each therapy session.

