The main hypothesis of the proposed study is that conjoint therapy will gradually promote affect regulation of both partners in orchestration; i.e., improvement in one partners' ability to regulate emotions will have a positive effect in the other partner's ability to regulate emotions. If the outcome of this project supports this hypothesis, these results will provide biologically interpretable and quantitative grounds for the effectiveness of conjoint therapy and pave the way for more comprehensive and large scale effectiveness studies, which, in turn, may establish conjoint therapy as a strategy that will complement "parallel track" treatment in preventing and diminishing IPV.

The physiological processes that were found to link attachment and affect regulation include parasympathetic regulation of heart rate and Hypothalamic Pituitary Adrenal (HPA) axis activity (Beauchaine, 2001; Böhnke, Bertsch, Kruk, & Naumann, 2010; Porges, 2001). There is increasing evidence for the role of HPA axis in the development and enhancement of aggressive behavior in youth as well as adults. Furthermore, cardiac vagal tone, a common physiological marker of the regulation of the Parasympathetic Nervous System (PNS), is correlated with both anxious and disruptive behaviors (Böhnke, Bertsch, Kruk, & Naumann, 2010; Porges, 2001). Putting these observations together, the proposed research further hypothesizes that, through promotion of affect regulation, attachment based couple therapy will enhance regulation of PNS and HPA activity in couples, which in turn will have a diminishing effect on IPV.

In summary, the proposed research integrates research findings on the links between couple therapy, affect regulation, physiological markers of emotion regulation, and IPV to hypothesize and test a novel psychophysiological model for the mechanisms of change induced by couple therapy in the context of IPV.

Target Subject Population

Subject population:

Inclusion criteria:

- 1) This study is open to married, dating, and cohabiting couples.
- 2) Couples will have to be involved in an intimate relationship for at least one year with the current partner.
- 3) Both partners have to be older than 18 years of age at the time they signed the consent form.
- 4) Couples must have mild to moderate forms of situational couple violence.

Principal Investigator: [name]

Protocol Summary for IRB: Feasibility Study of Couple Therapy Treatment for Situational Couple Violence (IRB# 09-13-27)

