Table 2. Assessment schedule

Principal Investigator: [name]

Protocol Summary for IRB: Feasibility Study of Couple Therapy Treatment for Situational Couple Violence (IRB# 09-13-27)

Efficacy & Data Analysis

Data analysis plan

This study is designed to be an initial feasibility study to collect pilot data in pursuit of the following aims:

Aim 1: After the first wave of data collection (pretest), the cross sectional relations among the basic constructs of interest will be examined. These basic constructs are psychophysiological markers of emotion regulation and IPV. In order to understand how these markers are related to violence, t-tests will be used to understand this effect. Each partner's HPA and PNS activity is expected to be directly linked to the violence perpetrated by their partner.

Aim 2: The objective of this aim is to understand whether violence decreases over time following therapy and whether this decrease is accompanied by respective change in physiological markers of emotion regulation. For this purpose, series of chi-square-test will be used as well as qualitative analysis.

Aim 3: In order to represent the interaction between the emotion regulation of partners, links from emotion regulation of each partner to the emotion regulation of the other partner at the next time point are included. Qualitative analysis with a grounded theory approach will be used.

The proposed sample size (8 couples) is chosen as a tradeoff between data collection time and statistical power. Since this is a feasibility study, we chose to start with a small sample size. GPower was used to estimate statistical power for the primary hypotheses. Assuming 8 couples (16 participants), with 4 couples in each group and two waves of data each, the statistical significance can be detected. Specifically, with power = .40, this study can detect an effect size of $f = .80$ (Using t-test statistics). Also chi-square test will be used to test the effectiveness of the intervention with power = .40. With this level of power, this study can detect an effect size of $f = .60$ (Using chi-square statistics).

The PI will continually monitor the study design to determine if there is a need to make modifications or discontinue the study due to lack of efficacy from therapeutic intervention.

Safety

Compensation for research related injury

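### The main hypothesis concerns one partner's emotion regulation acting on the other's; support for it is taken as grounds for effectiveness, with no violence outcome and no untreated comparison

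*Combined protocol and SAP*

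**What the plan says.** All references are to the combined protocol and SAP.

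- **Purpose** (under Study Design & Objectives) sets the question: "The purpose of this study is to understand whether the couple therapy that is used in practice is effective in preventing situational couple violence".
- **Hypotheses**, first paragraph, expects therapy to promote regulation in both partners together and explains this as: "improvement in one partners' ability to regulate emotions will have a positive effect in the other partner's ability to regulate emotions". The next sentence makes a conditional promise. If the project supports this hypothesis, "these results will provide biologically interpretable and quantitative grounds for the effectiveness of conjoint therapy". The same sentence goes on to larger effectiveness studies, which may later give conjoint therapy a place beside parallel-track treatment.
- **Hypotheses**, second paragraph, adds a separate hypothesis: "attachment based couple therapy will enhance regulation of PNS and HPA activity in couples, which in turn will have a diminishing effect on IPV".
- **Purpose, Aim 3**, is headed: "Examine the longitudinal effects of partners' psychophysiological regulation on each other's psychophysiological regulation and on IPV".
- **Data analysis plan, Aim 3**, says what will be done: "links from emotion regulation of each partner to the emotion regulation of the other partner at the next time point are included". The method named is qualitative analysis on a grounded theory approach.
- **Data analysis plan, Aim 2 and sample-size paragraph**: chi-square tests and qualitative analysis address whether violence falls over time after therapy, and a chi-square test is to examine the intervention's effectiveness. The text does not say which outcome that test uses or what is compared with what.
- **Study Design**: eight couples are randomised, four to immediate therapy (Group 1) and four to therapy after an 8-week wait (Group 2).

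**The concern.** The condition for claiming grounds for effectiveness and the meaning of effectiveness are two different things. The condition is a relation inside the couple: better regulation in one partner helps the other. The meaning, from the Purpose section, is that violence is prevented. A relation of the first kind may exist in couples who receive no therapy, and it may be found while violence stays where it was. Support for it therefore cannot, by itself, show that the therapy works.

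At stake is the reading of the results. If Aim 2 found no fall in violence but co-regulation appeared to be present, the Hypotheses section would still allow the report to say that there are quantitative grounds for the effectiveness of a treatment for violent couples.

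**Working it through.** The plan attaches no figure to this claim, so the check is mainly a reading of the text.

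**Step 1. Set the condition beside the question.**

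| Element | Main hypothesis (Hypotheses) | Aim 3 analysis (Data analysis plan) | Effectiveness (Purpose) |
|---|---|---|---|
| Outcome | Emotion regulation of the partner | Emotion regulation of the partner at the next time point | Situational couple violence |
| Violence term | None | None | Yes |
| Treated v not yet treated | None in the clause that spells it out | None | Implied by asking whether therapy prevents violence |
| Method | Results called quantitative | Qualitative | Not stated there |

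The Aim 3 heading does mention IPV, but the analysis written for Aim 3 does not carry it through. The promise of quantitative grounds is also at odds with an analysis that is only qualitative.

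**Step 2. Go through the possible results.**

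| Main hypothesis supported? | Violence lower than in the wait-list group? | What the Hypotheses sentence licenses | Answer to the Purpose question |
|---|---|---|---|
| Yes | Yes | Grounds for effectiveness | Favourable |
| Yes | No | Grounds for effectiveness | Not favourable |
| No | Yes | Nothing | Favourable |
| No | No | Nothing | Not favourable |

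The licence depends on the first column alone. The second row is the error, since the claim is permitted although the study's own question is not answered favourably. In the third row the sentence is merely silent.

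**Step 3. Illustrate why a partner link is not a treatment effect.** Every value here is assumed; none comes from the documents. Let each partner's regulation at the next step be 0.4 × own value + b × partner's value + θ + noise, where b is the partner link and θ is a shift due to therapy. Simulating 200,000 couples over 8 steps gave:

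| True link b | Therapy shift θ | Estimated link | Mean regulation at the end |
|---|---|---|---|
| 0 | 0 | -0.003 | 0.003 |
| 0 | 0.3 | 0.003 | 0.500 |
| 0.3 | 0 | 0.298 | 0.003 |
| 0.3 | 0.3 | 0.299 | 0.941 |

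The means agree with the formula θ × [1 − (0.4 + b)^8] / [1 − (0.4 + b)]. For b = 0 this is 0.3 × (1 − 0.0007) / 0.6 = 0.500. For b = 0.3 it is 0.3 × (1 − 0.0576) / 0.3 = 0.942.

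In this model the link is the same with and without a therapy effect, and a therapy effect can occur with no link. If therapy instead changed b itself, as Aim 3 suggests it might, that would show only in a comparison of treated with not-yet-treated couples. The model contains no violence variable, so it says nothing about violence in either direction.

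**Step 4. Check whether the design could supply the missing comparison.** It can.

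- Allocation is randomised, 4 v 4 couples (Study Design).
- Group 2 is assessed before the wait, and the physiological and behavioural collection is repeated when it moves to therapy (Study Design).
- IPV questionnaires are completed at each visit (Behavioral Measures).
- Group 1's post-test falls about 8 + 1 = 9 weeks after therapy starts (± 5 days). Group 2's wait is 8 weeks (± 10 days). The two time points are close.

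The gap is therefore in the stated inference and the written analysis, not in the data collected.

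**The case against.** The strongest reply is that the sentence is rationale in an IRB summary and not a decision rule. The Data analysis plan calls the work an initial feasibility study to collect pilot data. Aim 2 asks about violence over time, a chi-square test of effectiveness is planned, and the second paragraph of Hypotheses brings in IPV. All of this is correct, and it means that violence is not missing from the study. It does not mend the sentence, because none of these elements is made part of the condition on which the effectiveness claim depends.

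A second reply is that the hypothesis opens by saying therapy will promote regulation, so a therapy effect is included. It is asserted there, but the Aim 3 analysis does not test it against the wait-list group. Even if it did, violence would still be absent.

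Three stronger readings are tempting, and the documents do not support them:

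- A reader might infer that two partners who get worse together would count as support. The hypothesis is worded as improvement, so joint worsening would contradict it, and no section makes a positive correlation the criterion of support.
- A reader might infer that this study alone could recommend conjoint therapy beside parallel-track treatment. That role is left to later, larger studies and is hedged.
- A reader might infer that The Contribution of the Current Study makes the same mistake where it says "the results of this study will provide quantitative and objective evidence on the effectiveness of couple therapy". That sentence is conditional on success, and the text before it names the link between therapy and a decline in violence, studied with self-report data as well. It need not change.

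**Conclusion.** The concern holds in a narrow form. Support for the main hypothesis, as spelled out, is not evidence that the therapy prevents violence, because the condition has neither a violence outcome nor a comparison with couples not yet in therapy. The Aim 3 analysis adds neither. The fault lies in this one inference and not in the study as a whole.

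No numerical size can be given. The documents state no threshold for support of Aim 3 and no expected strength of the partner link, and the simulated values above illustrate the logic only. The practical consequence is the second row of the results table: a claim of grounds for effectiveness that would survive a finding of no fall in violence.

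The conclusion rests on two readings: that the explanatory clause defines the main hypothesis, and that effectiveness means what the Purpose section says. The statement that no new data are needed assumes that IPV is recorded for Group 2 at the end of the wait, before the first therapy session, as the pre-test definition and Behavioral Measures together imply.

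**What to change.** Two edits are needed.

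1. **Hypotheses.** Replace the effectiveness sentence with wording such as: *Support for this hypothesis will be reported as a possible mechanism of change, together with the direction of change in each partner's regulation and in IPV. It will not by itself be taken as evidence that conjoint therapy is effective.*
2. **Data analysis plan.** Tie any effectiveness statement to the randomised difference in IPV between Group 1 at post-test and Group 2 at its reassessment at the end of the wait, before therapy. Analyse it with the couple as the unit, give it with its interval, and label it exploratory. State that Group 2's reassessment precedes its first session, and that the comparison is with couples not receiving couple therapy, since Group 2 is taught safety planning and stress and anger management during the wait.

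The cost is modest: no added visits, measures or couples, but the analysis plan must be edited as well as the rationale, because it now writes out no Group 1 versus Group 2 contrast.

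A result on mechanism alone will support a weaker claim, and the randomised comparison will be imprecise. For a simple difference of means with 4 couples per group (6 degrees of freedom, t = 2.447), the 95% half-width is 2.447 × √(1/4 + 1/4) = 1.73 between-couple standard deviations, assuming equal variances, roughly normal couple-level values and no dropout. That is why the exploratory label is needed.
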